8.0 STUDY ASSESSMENTS/MEASUREMENTS AND PROCEDURES

8.1 Primary Assessments

- Range of liver stiffness in subjects with a surgically created total cavopulmonary connection

8.2 Primary Assessment Measurement

- Liver stiffness as determined by ultrasound shear wave elastography
- Liver stiffness as determined by magnetic resonance elastography

8.3 Additional Measurements

- Evaluate serum biomarkers of heart failure, brain type natriuretic peptide (BNP) and n-terminal BNP (NT-BNP)
- Evaluate biomarkers of liver fibrosis
- Proteomic and transcriptomic analyses on subcohorts of patients with the following:
 - Low levels of liver stiffness
 - Very high levels of liver stiffness
 - Decrease in liver stiffness with udenafil treatment

9.0 PLANNED STATISTICAL ANALYSES AND STATISTICAL CONSIDERATIONS

9.1 Statistical Analysis Plan

A Statistical Analysis Plan (SAP) will be developed and finalized prior to database lock. The SAP will contain detailed descriptions of data conventions and statistical procedures. Any deviation(s) from the SAP will be described and justified in the clinical study report.

9.2 Sample Size Determination

Given the primary outcome is descriptive, sample size estimate is provided for secondary outcome 1 – evaluating the change in liver stiffness before and after udenafil treatment compared to a patient receiving on-going udenafil treatment. Elastography indices measured by US or MRI elastography from baseline to 12 months will be examined in both udenafil treatment groups (U+ and U-), using paired t-test or Wilcoxon signed- rank test, as appropriate. DiPaola et al. (17) demonstrated that liver stiffness measured by US-SWE significantly increased from baseline to 6-month post-TCPC (mean $1.18 \pm SD 0.29$ m/s to 2.08 ± 0.24 m/s, $p<.0001$).

Assuming a mean liver shear wave speed (SWS) of 2.08 with known SD 0.24 as our baseline liver stiffness, a total sample size of 24 subjects (12 per group) is required to achieve 85% power with alpha=0.05 to detect 10% reduction of liver stiffness (deemed clinically meaningful in an individual) at 12 months from baseline in the U- group. Assuming a maximal enrollment of 100 subjects, (approximately 50% of whom will be from the FUEL U- cohort), we would be powered to detect a difference of 3.75% reduction in liver stiffness.

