3.0 BACKGROUND INFORMATION AND RATIONALE

3.1 Discussion of Hepatic fibrosis and FUEL Trial Extension Study

3.1.1 FALD

Fontan-associated liver disease (FALD) is defined as abnormalities in liver structure and function resulting from the abnormal circulation created by the total cavopulmonary connection (TCPC) and not related to any other process (1). FALD is increasingly recognized as one of the most common complications of the TCPC (2, 3) and one which is universally present in patients with TCPC physiology (8-11). After the Fontan operation, blood from the inferior and superior vena cava are routed directly to the pulmonary arteries bypassing the heart (Figure 1). In this circulation, blood is not “pumped” through the lungs but is “pushed” through by chronic elevation of the central venous pressure. It is postulated that the Fontan’s elevated, non-phasic systemic venous pressure results in obligate chronic hepatic venous hypertension and congestion that is likely an important driver of hepatic fibrosis. As part of the injury response, activated myofibroblasts deposit excess extracellular matrix in the perisinusoidal space, a process which, if it persists, can lead to increased hepatocellular injury, progressive fibrosis, organ dysfunction, and, ultimately, to cirrhosis and hepatic failure. The congestion and fibrosis result in a wide spectrum of liver disease, including synthetic dysfunction, ascites, portal hypertension, cirrhosis, and hepatocellular carcinoma, and may culminate in fulminant liver failure. The severity of liver fibrosis is known to increase with time after TCPC and occurs in the absence of any other identifiable etiology of chronic liver disease.

Figure 1: Description of Fontan Associated Liver Disease

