Receiver operating characteristic (ROC) areas under the curve for discriminating Ishak fibrosis scores “0-2” (no/mild fibrosis) from “3-6” (moderate/severe fibrosis) were 0.84 and 0.86 for point and 2D ultrasound SWE, respectively. In a recent prospective longitudinal observation study, we have shown that children with single ventricle congenital heart disease experience marked liver stiffening immediately after the TCPC. Five subjects returned at a mean of 185 ± 28 days, and mean liver stiffness remained elevated above baseline but with a variable response between patients when comparing the change in stiffness from early (2.5 and 7.5 days post-op) to late (6 month post-op) time points, which may reflect individual differences in cardiovascular performance or functional reserve (Figure 3).

Figure 3: Individual profile plots from subjects undergoing stage 3 Fontan palliation

[figure not shown]
These plots show changes in liver shear wave speed (stiffness) over time (follow #1 = 2.5 days post-op, follow-up #2 = 7.5 days post-op, and follow-up #3 = 185 days post-Fontan).

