6.2 Clinical Trial Population Characteristics

In order to be eligible for the clinical trial, subjects must fulfill the following criteria. Male and female subjects 12-19 years of age who meet all the Inclusion criteria and none of the Exclusion criteria will be enrolled.

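### Section 9.2 uses an SD of stiffness level as the known SD of 12-month change, so neither the 85% power nor the 3.75% detectable reduction is established

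*Combined protocol and SAP*

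**What the plan says.** Section 9.2 explains that the primary outcome is descriptive and gives a sample size for secondary outcome 1 instead. Change from baseline to 12 months is to be tested within each group (U+ and U-) by a paired t-test or a Wilcoxon signed-rank test.

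The inputs come from an earlier study, where the reported values are 1.18 (SD 0.29) before and 2.08 (SD 0.24) m/s after. Section 9.2 summarises that study by saying that "liver stiffness measured by US-SWE significantly increased from baseline to 6-month post-TCPC". It then carries the later value into its own calculation, taking a mean of 2.08 m/s "with known SD 0.24 as our baseline liver stiffness". From this it derives a requirement of 12 per group, 24 in all, for 85% power at the 0.05 level. The effect behind that number is stated as follows: "to detect 10% reduction of liver stiffness (deemed clinically meaningful in an individual) at 12 months from baseline in the U- group". The section adds that with 100 subjects, about half of them U-, a 3.75% reduction could be detected. It states no power for that second figure.

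Section 6.1 expects 50 to 150 subjects, and Section 5.0 expects about half to be U-, so about 25 to 75 U-.

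**The concern.** The power of a paired test depends on how much individual subjects' changes vary, not on how much subjects differ from one another at one visit. By the plan's own label, 0.24 is an SD of level. The protocol nowhere gives an SD of 12-month change, a correlation between visits, or the number of subjects behind the 0.24. Calling it known also removes the allowance for estimating the SD, which the named t-test makes.

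This is the only power statement in the plan, and it supports the aim on the effect of udenafil (Section 4.3, Secondary Aim 1). If the U- group shows no clear change, readers will judge that result against the claimed ability to see a reduction as small as 3.75%. If that ability was never established, a null result could be read as stronger evidence of no effect than it is.

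**Working it through.** **Inputs.** From 9.2: mean 2.08 m/s, SD 0.24, target reduction 10% = 0.208 m/s, second target 3.75% = 0.078 m/s, alpha 0.05. Two-sided testing is assumed, because 9.2 does not say and it is what reproduces the plan's figure. U- numbers: 12 (9.2), 50 (9.2, half of 100), 25 and 75 (half of 50 and 150). The correlation rho is not given, so a range of 0 to 0.8 is assumed.

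**Reproducing the plan's figure.** Paired z formula with a known SD of change:

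n = (SD × (1.960 + 1.036) / delta)² = (0.24 × 2.996 / 0.208)² = 11.95, rounded up to 12, with power 85.1%.

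This matches. Other readings do not. One-sided z gives n = 10. A two-sample comparison of levels needs 24 per group. The two-sided paired t-test (noncentral t) has 78.0% power at n = 12 and needs 15 (n = 14 falls just short, at 84.99%). So 0.24 was entered as the known SD of within-subject change.

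**Two separate effects.** The drop from 85% to 78% comes from z versus t alone and has nothing to do with correlation. The second effect is the substitution of a level SD for a change SD. If both visits have SD 0.24,

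SD of change = 0.24 × √(2(1 − rho)),

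which equals 0.24 only when rho = 0.5. That condition needs equal SDs at the two visits. The earlier study's SDs were 0.29 and 0.24, so even this is an assumption.

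**Two-sided paired t-test over the range:**

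| rho | SD of change | Power for 10%, n = 12 | n for 85% | Power for 10%, 25 U- | Power for 10%, 50 U- | Reduction detectable at 85%, 50 U- |
|---|---|---|---|---|---|---|
| 0 | 0.339 | 49% | 26 | 84% | 99% | 7.1% |
| 0.25 | 0.294 | 61% | 20 | 92% | >99% | 6.1% |
| 0.5 | 0.240 | 78% | 15 | 99% | >99% | 5.0% |
| 0.8 | 0.152 | 99% | 7 | >99% | >99% | 3.2% |

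**The 3.75% figure.** With 50 U- and SD 0.24, the z formula gives a detectable reduction of 0.24 × 2.996 / √50 = 0.1017 m/s, and 0.1017 / 2.08 = 4.89% at 85% power (4.57% at 80%). Power for 3.75% is 63% by z and 62% by paired t. Reaching 85% for 3.75% with 50 U- needs an SD of change of about 0.180, that is rho of about 0.72 with level SD 0.24. The 12-per-group figure implies rho = 0.5, so the two statements in 9.2 do not rest on the same input.

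**Margin for the 10% target.** The largest SD of change that keeps 85% power by paired t is 0.219 at n = 12, 0.333 at 25 U-, 0.481 at 50 U- and 0.593 at 75 U-.

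**The case against.** The best defence is that 12 per group is a computed minimum, not the planned size. The trial expects 25 to 75 U- subjects, enrolment is set by the parent trial's pool, and the primary outcome is descriptive. At those numbers the 10% target is nearly safe even with no correlation between visits. The 12 per group is also not an arithmetic slip, since it reproduces under the formula used. All of this stands, and it confines the practical damage to the stated 85% and, above all, the 3.75% figure.

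Three stronger readings are tempting, and the documents do not support them.

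- *That the 0.24 comes from five children and so is almost uninformative.* Section 3.2.2.1 describes the group's own study after TCPC, where "Five subjects returned at a mean of 185" days, and the timing matches. But that paragraph cites no source and does not give 2.08 or 0.24, and 9.2 gives no n. A confidence interval for the SD based on n = 5 would rest on a guess. Feeding its limits in as SDs of change would also repeat the substitution criticised here.
- *That true power is below 85%.* The substitution has no fixed direction. With rho above 0.5 the SD of change is smaller than 0.24. Only the z-for-t effect is one-sided.
- *That the source population is shown to be wrong.* Section 6.2 enrols "Male and female subjects 12-19 years of age", and Section 3.1.1 says "The severity of liver fibrosis is known to increase with time after TCPC". That sentence concerns severity, not the SD of change. The documents give neither the age of the source cohort nor the time since TCPC of this one. The different stage is a reason for caution about 0.24, not proof of error.

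**Conclusion.** The concern holds as an unsupported input. Section 9.2 does not establish 85% power at 12 per group: the named paired t-test gives 78% with the plan's own SD, and 49% to 99% for rho from 0 to 0.8. The effect on the 10% target is small at planned enrolment, with at least 84% power at 25 U- and 99% at 50 U- over that range. The 3.75% claim does not follow from the stated inputs. It has about 62% power with 50 U- at SD 0.24, and would reach 85% only if rho were about 0.72 or higher.

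A reader might infer that the study is underpowered, but the documents do not show that. They show that its sensitivity to small reductions is unknown. These figures assume two-sided alpha 0.05, normally distributed changes, a level SD of 0.24 at both visits, half of subjects U-, and no dropout. A larger level SD in this cohort would lower all of them.

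**What to change.** In Section 9.2:

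1. Delete the word known. State that 0.24 is an SD of level at about 6 months after TCPC, and give the number of subjects behind it.
2. Base the calculation on the SD of within-subject change and on the paired t-test. If the earlier cohort has repeat scans, take the SD from its paired differences.
3. Replace the single 85% and 3.75% figures with power for a 10% reduction, and the reduction detectable at a stated power, over a stated range (for example rho 0 to 0.8) at 25, 50 and 75 U-. State the sidedness.
4. Give no confidence interval for the SD based on five subjects unless that source n is confirmed.

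The cost is protocol wording, and the same text can go into the SAP, which Section 9.1 says is still to be developed and finalized before database lock. The headline figures become a less favourable range. No extra patients, visits or scans are needed.

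### Section 9.2: the 85% power at 12 per group fits a two-sided z-test with known SD; if testing is two-sided, the paired t-test named there has 78% on the same inputs

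*Combined protocol and SAP*

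**What the plan says.** Section 9.2 justifies the sample size through Secondary Aim 1, because the primary outcome is descriptive. Change from baseline to 12 months is to be examined in both treatment groups "using paired t-test or Wilcoxon signed- rank test, as appropriate". The inputs come in the next paragraph: "Assuming a mean liver shear wave speed (SWS) of 2.08 with known SD 0.24 as our baseline liver stiffness". From these the section concludes that "a total sample size of 24 subjects (12 per group) is required to achieve 85% power with alpha=0.05", the target being a 10% reduction at 12 months in the U- group.

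The section does not give the sidedness of the test, the SD of the within-subject change, the baseline-to-12-month correlation, or the formula. Section 6.1 projects 50 to 150 subjects, and Section 5.0 expects about half of those eligible to be U-.

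**The concern.** The test named for the analysis and the calculation behind the sample size do not appear to match. A paired t-test estimates the SD from the differences, with only 11 degrees of freedom when n is 12. A calculation that treats the SD as known omits that cost, and at this sample size the cost is several points of power.

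What is at stake is whether the stated figure is accurate. This is the only sample-size justification in the document. If testing is two-sided, the chance of missing the reduction that the plan calls clinically meaningful is 22% at 12 per group with the t-test, and about 26% with the Wilcoxon test, against the 15% implied.

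**Working it through.** **Inputs, all from Section 9.2.** Mean 2.08 m/s, SD 0.24, reduction 10%, alpha 0.05, power 85%, 12 per group. No dropout allowance is stated and none is applied.

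**Effect size.** 10% of 2.08 is 0.208 m/s, and 0.208/0.24 = 0.867.

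**SD of change.** The plan gives 0.24 as the SD of baseline stiffness. With equal SDs at both visits and correlation r, the SD of change is 0.24 × √(2(1 − r)). This equals 0.24 only when r = 0.5, so using 0.24 for paired differences implicitly assumes that value.

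**Reproducing the plan's figure (z-test, SD known).**
- Two-sided: n = ((1.960 + 1.036)/0.867)² = 11.95, so 12. Power at 12 = Φ(0.867 × √12 − 1.960) = Φ(1.042) = 85.1%. Both the n and the power match.
- One-sided: n = ((1.645 + 1.036)/0.867)² = 9.57, so 10. This does not match.
- A two-sample comparison of U- with U+ at 12 per group has 56.5% power by z and 52.8% by t, so it is not the source of the 85%.

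**The named tests.** Paired t power comes from the noncentral t distribution with n − 1 degrees of freedom and noncentrality 0.867 × √n. At n = 12 the noncentrality is 3.00. Exact Wilcoxon signed-rank power comes from 400,000 simulated samples of normal differences at each n.

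| n per group | z, two-sided | paired t, two-sided | Wilcoxon, two-sided | paired t, one-sided | Wilcoxon, one-sided |
|---|---|---|---|---|---|
| 11 | 82.0% | 73.6% | not run | 84.8% | not run |
| 12 | 85.1% | 78.0% | 73.8% | 87.8% | 85.6% |
| 13 | 87.8% | 81.8% | 79.6% | 90.3% | 88.4% |
| 14 | 90.0% | 84.99% | 83.5% | 92.3% | 90.3% |
| 15 | 91.9% | 87.7% | 85.9% | 93.9% | 92.5% |

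The two-sided Wilcoxon at n = 12 has an attained alpha of 0.0425, because its null distribution is discrete. An efficiency approximation (12 × 3/π = 11.46 effective subjects) puts its power at 75.7%.

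**Sensitivity to the SD of change.** Two-sided paired t power at n = 12 is 49% for an assumed r of 0, 64% for 0.3, 78% for 0.5, 86% for 0.6 and 94% for 0.7.

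**Planned enrolment.** A total of 50 to 150, half of them U-, gives about 25 to 75 U- subjects. Two-sided paired t power for the 10% reduction at n = 25 is 98.6% with the SD of change at 0.24.

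**The case against.** The strongest reply concerns sidedness. Section 9.2 says only "85% power with alpha=0.05", the hypothesis for Secondary Aim 1 in Section 4.3 is directional, and the calculation is for a reduction. Under one-sided 0.05 the paired t-test has 84.8% power at 11 and 87.8% at 12, so 12 is exactly the smallest number that reaches 85%. The Wilcoxon also passes, at 85.6%. On that reading there is no shortfall. This stands as a condition on the point. It does not remove it: one-sided testing is stated nowhere, and it leaves the description of the SD as known without a role.

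The z-test attribution is itself an inference. Calling the SD known may simply mean that it was taken from the published study cited just before. The 3.75% detectable reduction later in the section does not settle the matter. At 50 U- subjects and 85% power, two-sided z gives 4.89%. A value near 3.75% appears only with 100 subjects and 90% power, where z gives 3.74% and t gives 3.78%, so it hardly separates the two methods.

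The third reply is that the unstated SD of change matters more than the choice between z and t. That is correct: the range from 49% to 94% dwarfs a 7-point gap, and any restated figure must carry its SD assumption openly.

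Finally, the Wilcoxon figures assume normal differences, where that test would be the less likely choice. They should be read as indicative.

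**Conclusion.** The point holds, conditionally. If testing is two-sided at 0.05 and 0.24 is the SD of the paired change, the stated 85% at 12 per group is not the power of either named test: it is 78% for the paired t-test and about 74% for the exact Wilcoxon. The t-test needs 14 per group to reach 85% to the nearest percent (84.99%), or 15 to exceed it (87.7%). The Wilcoxon needs about 15. If testing is one-sided, 12 is sufficient and the defect is only that the plan does not say so.

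A reader might infer two stronger things. One is that the arithmetic is plainly wrong. The documents do not support that, because the sidedness and formula are not given and one permissible reading yields 12. The other is that the study is underpowered for Secondary Aim 1. This point does not show that either: the lower end of planned enrolment gives about 25 U- subjects and 98.6% power on the same inputs. What is wrong is the stated minimum. This is a minor point.

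**What to change.** In Section 9.2:

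- State the sidedness of the test.
- State that 0.24 is being used as the SD of the 12-month change, which implies a correlation of 0.5 between visits if the SDs are equal.
- Give the figure for the named test. For a two-sided paired t-test, write either 14 to 15 per group for 85% power, or 12 per group with 78% power. If the Wilcoxon test is to be the basis, write about 15 per group.
- If one-sided 0.05 was intended, say so and remove the description of the SD as known.
- Compute the detectable reduction at planned enrolment by the same t-based method, and state its power and number of subjects. For example, 50 U- subjects at 85% power, two-sided, gives about 5.0% with an SD of change of 0.24.

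The cost is a few sentences. Enrolment, visits and measurements are unchanged. Under two-sided testing, the stated figure becomes slightly less favourable.

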1.0 PROTOCOL SYNOPSIS

TITLE OF STUDY	AN IMAGING AND BIOMARKER EVALUATION OF HEPATIC STIFFNESS IN CHILDREN ENROLLED IN THE FONTAN UDENAFIL EXERCISE LONGITUDINAL STUDY
PHASE	Open Label Extension
STUDY OBJECTIVE	Determine scope of hepatic stiffness in Fontan patients by ultrasound and magnetic resonance imaging elastography and evaluate the efficacy of udenafil in reducing liver stiffness.
SIGNIFICANCE	Study will obtain necessary and broad information regarding hepatic stiffness in Fontan patients and will be the first to evaluate a potentially efficacious treatment to reduce liver stiffness.
STUDY DESIGN	Prospective cohort study integrated with the Fontan Udenafil Exercise Longitudinal (FUEL) clinical trial
PLANNED SAMPLE SIZE	50-150 Subjects
KEY SUBJECT SELECTION CRITERIA	
Inclusion Criteria:
 
1. Enrollment in FUEL Extension Trial2. Informed assent from subject, informed consent from parent/legal guardian as appropriate 
Exclusion Criteria:
 
1. Non-enrollment in the FUEL Extension Trial2. Subjects with contra-indications for MRI (these subjects will be excluded from the MRI component of this study)3. Other exclusionary criteria will match those used for the FUEL Extension Trial
TREATMENT	One year of udenafil treatment (87.5 mg twice daily)
PRIMARY AIM	Define the range of liver stiffness in those who have had the surgical creation of a total cavopulmonary connection.

SECONDARY AIMS:	
• Determine the impact of udenafil treatment on liver stiffness in a large cross-section of adolescents who have undergone total cavopulmonary connection.• Determine the relationship between clinical outcomes and liver stiffness.• Assess the association between biomarkers of both heart failure and liver fibrosis and liver stiffness.
EFFICACY PARAMETERS	Reduction in liver stiffness after initiating udenafil therapy adolescents with Fontan physiology.
EFFICACY ASSESSMENTS	Efficacy will be assessed at FUEL-OLE initiation and conclusion.
EFFICACY ENDPOINTS	Absolute liver stiffness as measured by ultrasound (and MR) and change in liver stiffness.
SAFETY PARAMETERS	As this study has no active intervention, there are no specific safety measures beyond FUEL-OLE protocols.
SAFETY ASSESSMENTS	As this study has no active intervention, there are no specific safety assessments beyond FUEL-OLE protocols.

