4.3 Secondary Aims and Hypotheses

Secondary Aim 1: Determine the impact of udenafil treatment on liver stiffness in a large cross-section of adolescents who have undergone total cavopulmonary connection.

Hypothesis: Udenafil treatment will reduce liver stiffness as measured by non-invasive elastography by decreasing venous congestion.

Secondary Aim 2: Determine the relationship between clinical outcomes and liver stiffness.

Hypothesis: Liver stiffness will be associated with measures of ventricular diastolic function, exercise performance, and endothelial function.

Secondary Aim 3: Assess the association between biomarkers of both heart failure and liver fibrosis and liver stiffness.

Hypothesis: Biomarkers of heart failure and liver fibrosis will directly correlate with liver stiffness as measured by ultrasound and magnetic resonance elastography.

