6.0 SELECTION AND DISPOSITION OF SUBJECTS

6.1 Number of Subjects

Subjects for this protocol will be recruited from the pool of patients in the FUEL Extension trial, from all participating centers that have the capacity to perform either ultrasound SWE or magnetic resonance elastography. We anticipate that we will have access to 100-200 subjects, although this will vary based on the start date for this study. If we achieve between a 50-75% consent rate, it would provide a sample size of 50-150 subjects.

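### The 3.75% detectable reduction in section 9.2 does not follow from its own inputs; with about 50 U- subjects at 85% power it is 4.4% to 5.0%

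*Combined protocol and SAP*

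**What the plan says.** The primary outcome is descriptive, so section 9.2 bases its sample size on secondary outcome 1, the change in liver stiffness from baseline to 12 months. It names a paired t-test or Wilcoxon signed-rank test within each group. The inputs are a shear wave speed of "2.08 with known SD 0.24 as our baseline liver stiffness" (m/s). From these it states that "a total sample size of 24 subjects (12 per group) is required to achieve 85% power with alpha=0.05" for a 10% reduction in the U- group.

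The next sentence reads "Assuming a maximal enrollment of 100 subjects, (approximately 50% of whom will be from the FUEL U- cohort"), and concludes that "we would be powered to detect a difference of 3.75% reduction in liver stiffness".

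The paragraph does not say whether alpha is one- or two-sided, does not repeat the power for the 3.75%, and gives no SD of change or within-subject correlation. The hypothesis in section 4.3 is directional: "Udenafil treatment will reduce liver stiffness as measured by non-invasive elastography". Planned enrolment in section 6.1 and the synopsis is 50 to 150, whereas section 9.2 treats 100 as the maximum.

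**The concern.** For a one-group paired comparison, the detectable change shrinks with the square root of the number of subjects. Going from 12 to 50 subjects roughly halves it, from 10% to about 5%. The plan's 3.75% is clearly smaller than that.

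This is the only sensitivity figure the protocol gives for its udenafil question at the expected enrolment. If it is too optimistic, a null result could be read as ruling out effects that the study could not reliably detect.

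**Working it through.** **Inputs (section 9.2).** Mean 2.08 m/s; SD 0.24 m/s; alpha 0.05; power 85%; 12 subjects per group for a 10% reduction; about 50 U- subjects for the 3.75% statement. A 10% reduction is 0.208 m/s and 3.75% is 0.078 m/s.

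**Assumptions.** The plan gives 0.24 as a baseline SD. I first use it as the SD of within-subject change, then drop that assumption. The 85% power is carried over to the 3.75% sentence, and 80% is tried as well.

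**Formulas.** For a z-test with known SD, n = [SD × (z_α + z_power)/δ]² and δ = SD × (z_α + z_power)/√n. For the paired t-test, power comes from the noncentral t distribution with n − 1 degrees of freedom and noncentrality δ√n/SD.

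**Step 1: reproduce 12 per group.** The two-sided z-test gives n = [0.24 × (1.960 + 1.036)/0.208]² = 11.95, so 12. Its power is 82.0% at 11 and 85.1% at 12. A one-sided paired t-test also has 12 as its smallest n (84.8% at 11, 87.8% at 12). A two-sided paired t-test needs 15 (78.0% at 12, 84.99% at 14, 87.7% at 15), and a one-sided z-test needs 10. The stated 12 is therefore reproducible under two conventions.

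**Step 2: the same conventions at 50 U- subjects.** For the two-sided z-test, δ = 0.24 × 2.996/√50 = 0.1017 m/s, which is 4.89% of 2.08.

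| Convention (SD of change 0.24) | Smallest n for 10%, 85% power | Detectable at n = 50, 85% | Detectable at n = 50, 80% | Power for 3.75% at n = 50 | n for 3.75% at 85% |
|---|---|---|---|---|---|
| Two-sided z | 12 | 4.89% | 4.57% | 63.2% | 86 |
| One-sided paired t | 12 | 4.44% | 4.11% | 73.3% | 70 |
| Two-sided paired t | 15 | 4.99% | 4.66% | 61.5% | 87 |
| One-sided z | 10 | 4.38% | 4.06% | 74.3% | 69 |

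No row gives 3.75% at n = 50, at either power.

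**Step 3: leave the SD free.** Take any SD for which 12 is the smallest n for a 10% reduction at 85% power, then compute the detectable reduction at n = 50.

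| Convention | SD range consistent with 12 | Detectable at n = 50, 85% |
|---|---|---|
| Two-sided z | 0.230–0.241 | 4.69–4.90% |
| One-sided z | 0.257–0.269 | 4.69–4.90% |
| One-sided paired t | 0.239–0.252 | 4.42–4.65% |
| Two-sided paired t | 0.207–0.219 | 4.31–4.55% |

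Conversely, the SD that yields 3.75% at n = 50 and 85% power is 0.180 (two-sided t), 0.184 (two-sided z), 0.203 (one-sided t) or 0.206 (one-sided z). With those SDs the 10% effect needs only 9 subjects (t) or 8 (z), not 12. No single SD supports both of the plan's figures.

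**Step 4: where a figure near 3.75% does appear.** With SD 0.24 and a two-sided test, 75 subjects at 80% power give 3.73% (z) or 3.78% (t), and 100 subjects at 90% power give 3.74% or 3.78%. Neither matches about 50 subjects at 85%. The 75 is half of the upper enrolment of 150 in section 6.1. This may hint at the source, but the documents do not settle it.

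**The case against.** **The figure may refer to the whole cohort.** The 3.75% sentence does not itself say U-, and the synopsis plans to assess change in the overall cohort as well as by group. With all 100 subjects as one paired group and 90% power, two-sided, 3.74–3.78% is attainable. But at the stated 85% power, n = 100 gives 3.46–3.49% two-sided or 3.09–3.12% one-sided, which again is not 3.75%. No 90% power appears anywhere in the plan, and giving the U- share would serve no purpose if all 100 were counted. It remains true that the group is inferred from context, so the corrected sentence should name it.

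**The SD of change is not given.** This is a fair point, and it affects the size of the discrepancy. If a two-sided paired t-test were used with an SD chosen so that 12 is the smallest n, the detectable reduction would be 4.3–4.5% rather than 5.0%, and power for 3.75% would be 70–74% rather than 62%. It does not affect the mismatch, as step 3 shows.

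**The point is small.** The outcome is secondary, enrolment is set by access and consent rather than power, and 4.4–5.0% is still at most half of the 10% change the plan calls clinically meaningful. This limits the weight of the point but does not make the stated figure correct.

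**Conclusion.** The concern holds. With about 50 U- subjects and 85% power, the detectable reduction is 4.4% (one-sided) to 4.9–5.0% (two-sided) if 0.24 is the SD of within-subject change. It is 4.3% to 4.9% for any SD that makes 12 the smallest sample for a 10% reduction. The conclusion rests on reading the sentence as a within-group figure for the U- subjects; the carried-over 85% power is not critical, since with SD 0.24 even 80% power gives at least 4.06%.

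At 50 U- subjects and SD 0.24, a true 3.75% reduction would be missed about 27% of the time one-sided, or 37–38% two-sided, against the 15% that 85% power implies. The 3.75% sets no enrolment target or decision rule, and the 10% target is safe: with 25 U- subjects, half of the lowest planned enrolment, its power is 98.6% by two-sided paired t-test. This should be corrected, but no analysis or recruitment depends on it.

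**What to change.** Replace the 3.75% with the detectable reduction from the same test, sidedness and power that underlie the 12 per group. State that convention, and name the U- group as the one it refers to. Label 0.24 as an assumed SD of within-subject change. Choose one of:

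- **(a) Two-sided z-test, SD known:** 12 per group; 4.9% detectable with 50 U-; 63% power for 3.75%.
- **(b) One-sided paired t-test:** 12 per group; 4.4%; 73%.
- **(c) Two-sided paired t-test:** 15 per group; 5.0%; 62%.

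Reconcile the maximum of 100 in section 9.2 with "50-150 Subjects" in the synopsis and the same range in section 6.1. If another enrolment was meant, give the figure for that number of U- subjects. At 85% power, 25 U- subjects detect 6.9% (a), 6.4% (b) or 7.2% (c); 75 U- subjects detect 4.0%, 3.6% or 4.05%.

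The cost is one reworded paragraph and a less favourable sensitivity statement. No extra patients are needed, and the 10% target and the analyses stay as they are. Only option (c) changes the stated minimum, from 24 to 30 in total, which is still below the lowest planned enrolment of 50.
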